7.5.5. Patient-Reported Outcome Measures

An electronic PRO system will be used during the study to allow patients to complete the study questionnaires.

In both the Phase 2 and Phase 3 parts of the study, each patient will complete the following PRO measures:

- MACrO₂
- QOL-B
- NTM Symptoms Module
- SGRQ-C
- Global assessment scales (Patient Global Impression of Severity [PGIS] and Patient Global Impression of Change [PGIC])

The Investigator will complete the Clinician Global Impression of Severity (CGIS) and Clinician Global Impression of Change (CGIC).

The PROs will be completed at the time points specified in the Schedule of Assessments ([Appendix A](#)). On Day 1, PROs should be completed prior to study drug administration, and will serve as the baseline assessment for comparison to on-treatment assessments. The MACrO₂, QOL-B, NTM Symptoms Module, SGRQ-C, and PGIS will be completed twice before the first

dose of study drug (ie, once between Days -14 and -7 and on Day 1 prior to study drug administration) to assess test-retest reliability. The MACrO₂ and PGIS will be completed at additional time points to further assess test-retest reliability. For patients whose EOT Visit coincides with the Month 3 or Month 6 visit, the MACrO₂ and PGIS will be completed 1 week (+1 day) after the EOT Visit. PRO test-retest reliability will be assessed in Phase 2 and may be analyzed in Phase 3 if deemed necessary.

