7.5.5.1. MACrO₂ Patient-Reported Outcome Measure

The MACrO₂ PRO will be psychometrically evaluated in a blinded manner in the Phase 2 part of the study and a formal psychometric analysis plan will be developed. The planned analyses will include item-level performance (distribution of responses, missing data, and floor and ceiling effects); construct validity (including known-groups and concurrent validity); test-retest reliability; sensitivity to change; and defining meaningful change thresholds (ie, using global anchor items and clinical outcomes to define response). The MACrO₂ PRO measure may be further refined following the psychometric analyses or embedded interviews. The selection of the final PRO measure to use as the primary endpoint (in the US) or key secondary endpoint (outside the US) in the Phase 3 portion of the study and the timing of this assessment will be based on the MACrO₂ PRO item performance and sensitivity to change by treatment outcomes.

Patients will complete all 7 symptom items from the MACrO₂ PRO measure ([Appendix C](#)) at all study assessment time points specified in the Schedule of Assessments ([Appendix A](#)), regardless of the presence or absence of symptoms. During the Day -14 to -7 Screening Visit and on Day 1 (prior to dosing), patients will select which symptom that they rated as moderate, severe, or extremely severe that they most want to see improved to help understand the “key” symptom for each individual patient (ie, via MACrO₂ PRO Item 8). The severity of all symptoms on Day 1, as well as the “key” symptom identified on Day 1, will be defined as the baseline assessment for determination of clinical response in postbaseline visits. Symptom-based clinical response is defined as improvement of ≥ 1 grade in the key symptom with no worsening of ≥ 1 grade of other symptoms, according to the MACrO₂ PRO.

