3.1.2 Definition of Baseline

For PRO data entered by the patient (MACrO₂, QOL-B, NTM Symptoms Module, SGRQ-C, or PGIS), baseline is defined as the last entry recorded by the patient on or prior to the first dose of study drug + 1 day (ePRO-specified close of window to further entry to patients).

For PRO data entered by the site (CGIS), baseline is defined as the last entry recorded by the patient on or prior to the first dose of study drug + 6 days (ePRO-specified close of window to further entry to sites).

For microbiological data, baseline pathogen(s) are determined based on MAC pathogens isolated from all MAC-positive respiratory samples collected within the 8-week Screening Period prior to the first dose of study drug, with specific representative baseline pathogen(s) confirmed by blinded Sponsor review.

For all other efficacy and safety endpoints, baseline is defined as the last measurement or assessment prior to first dose of study drug, including results from unscheduled visits if applicable.

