3.4.1 Phase 2 Efficacy Endpoints – Month 6 Analysis

3.4.1.1 Phase 2 Primary Efficacy Endpoint in the US (Secondary Endpoint Outside the US)

The primary efficacy endpoint in the US (secondary outside the US) is symptom-based clinical response assessed by MACrO₂ PRO between baseline and Month 3 and baseline and Month 6. While summary results for both of these visits will be generated in parallel, the Month 6 visit will be considered of primary interest with the Month 3 visit considered supportive. The Estimand corresponding to the primary endpoint is defined with the following five attributes:

1. Population: Randomized patients with MAC culture-positive Pre-Study and Screening respiratory specimens
2. Treatment: Epetraborole oral tablets 500 mg (two 250 mg oral tablets) QD + OBR or placebo oral tablets QD matched to epetraborole dosage + OBR
3. Variable: MACrO₂ PRO response rate at Month 3 and Month 6. MACrO₂ PRO response at the given time point is defined as improvement of ≥ 1 grade in the key symptom with no worsening of other symptoms compared with baseline MACrO₂ PRO assessment. The baseline MACrO₂ PRO assessment is defined as the last assessment prior to the first dose of study drug.
4. Intercurrent events:
 - a. New, additional non-study-specific, antimycobacterial therapy that is potentially effective against MAC for reasons other than clinical failure of study drug: data collected after such therapy will not be used and patients will be classified as a clinical failure for MACrO₂ PRO response (composite strategy)
 - b. Surgery for MAC lung disease for reasons other than clinical failure of study drug: data collected after such surgery will not be used and patients will be classified as a clinical failure for MACrO₂ PRO response (composite strategy)
 - c. Permitted medications/interventions or prohibited medications/interventions other than those described in bullets a and b: MACrO₂ PRO data collected after permitted or other prohibited medications/interventions administration will be used as recorded (treatment policy strategy)
 - d. Inadequate compliance: patient data will be used as recorded (treatment policy strategy)
5. Population-level summary: Difference between epetraborole + OBR and placebo + OBR in response rate in MACrO₂ PRO assessment at Month 3 and Month 6.

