3.4.3 Phase 3 Efficacy Endpoints

3.4.3.1 Phase 3 Primary Efficacy Endpoint in the US (Key Secondary Endpoint Outside the US)

The primary efficacy endpoint in the US (key secondary outside the US) is change from baseline to Month 6 in QOL-B respiratory domain score. The Estimand corresponding to the primary endpoint is defined with the following five attributes:

1. Population: Patients with MAC culture-positive Pre-Study and Screening respiratory specimens
2. Treatment: Epetraborole oral tablets 500 mg (two 250 mg oral tablets) QD + OBR or placebo oral tablets QD matched to epetraborole dosage + OBR
3. Variable: Change from baseline to Month 6 in QOL-B respiratory domain score. QOL-B respiratory domain score is measured on a scale from 0 to 100 (with higher scores indicating better health-related quality of life). The baseline QOL-B respiratory domain score assessment is defined as the last entry recorded or updated by the patient on or prior to the first dose of study drug + 1 day (ePRO-specified close of window to further entry to patients).
4. Intercurrent events:
 - a. New, additional non-study-specific, antimycobacterial therapy that is potentially effective against MAC for reasons other than clinical failure of study drug: data collected after such therapy will be set to the last available score from a visit prior to the start of therapy (composite strategy)
 - b. Surgery for MAC lung disease for reasons other than clinical failure of study drug: data collected after such surgery will not be used and results will be set to the last available score from a visit prior to surgery (composite strategy)
 - c. Permitted medications/interventions or prohibited medications/interventions other than those described in bullets a and b: QOL-B respiratory domain data collected after permitted or other prohibited medications/interventions administration will be used as recorded (treatment policy strategy)
 - d. Inadequate compliance: patient data will be used as recorded (treatment policy strategy)

5. Population-level summary: Difference between epetraborole + OBR and placebo + OBR in least squares mean change from baseline to Month 6 in QOL-B respiratory domain score.

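### The SAP lets a PRO entry made up to one day after first dose replace a valid pre-dose baseline, including for the Phase 3 US primary endpoint, contrary to Protocol 7.5.5

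*SAP*

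**What the plan says.** **Protocol.** Section 7.5.5 states: "On Day 1, PROs should be completed prior to study drug administration, and will serve as the baseline assessment". A footnote to the Schedule of Assessments (Table 3) likewise ties baseline to PRO entries made before first dose. The patient PROs (MACrO₂, QOL-B, NTM Module, SGRQ-C, PGIS) are scheduled twice before dosing, at Days -14 to -7 and on Day 1.

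**SAP, general rule.** For patient-entered PROs, Section 3.1.2 says "baseline is defined as the last entry recorded by the patient on or prior to the first dose of study drug + 1 day". For the site-entered CGIS the limit is "on or prior to the first dose of study drug + 6 days". The reason given in both cases is when the ePRO system closes the form. Apart from microbiology, which has its own rule, everything else stays strictly pre-dose: "baseline is defined as the last measurement or assessment prior to first dose of study drug".

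**SAP, US primary.** Section 3.4.3.1 repeats the one-day rule for QOL-B and adds that an updated entry counts: "the last entry recorded or updated by the patient on or prior to the first dose of study drug + 1 day".

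**SAP, Phase 2.** In the Phase 2 estimand (3.4.1.1), the MACrO₂ baseline "is defined as the last assessment prior to the first dose of study drug". Section 3.1.2, which covers both phases, says otherwise for the same instrument.

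**The concern.** A baseline should not be open to influence from randomized treatment. Under the SAP wording the latest entry in the window wins. There is no precedence for an entry made before dosing, and the post-dose part of the window is not confined to patients who lack one. A patient who completed the QOL-B before dosing and changed it the next day would be analysed on the changed value.

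That value enters the US primary analysis twice: it is subtracted to form the change score, and it is the ANCOVA covariate. Any early difference between arms, or any guess about assignment, could then pass into the treatment estimate. The same baseline rule feeds the MACrO₂ total scaled score, the PRO responder analyses, the MMRM and the time-to-response analyses.

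**Working it through.** The plan gives no figure that depends on this rule, so there is none to reproduce. The check is a comparison of texts, followed by an illustration of size under stated assumptions.

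**1. Definitions side by side**

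| Source | Applies to | Latest permitted baseline |
|---|---|---|
| Protocol 7.5.5 | PROs on Day 1 | before first dose |
| SAP 3.1.2 | patient-entered PROs | first dose + 1 day |
| SAP 3.1.2 | CGIS | first dose + 6 days |
| SAP 3.4.3.1 | QOL-B, US primary | first dose + 1 day, updates included |
| SAP 3.4.1.1 | MACrO₂, Phase 2 | before first dose |
| SAP 3.1.2 | other efficacy and safety, microbiology apart | before first dose |

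**2. Which entries can fall in the post-dose window.** After Day 1 the next scheduled QOL-B is at Month 1 (Day 29), and MACrO₂ is weekly. No scheduled on-treatment form falls within one day of first dose. A post-dose baseline therefore requires a Day 1 form that was completed late or edited.

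**3. Reach.** SAP 3.4 tests three endpoints in order in each region: QOL-B respiratory domain change, MACrO₂ total scaled score change, and culture conversion. Two of the three use this baseline rule. CGIS is in neither hierarchy; its baseline affects CGIS response and the covariate in the CGIS and CGIC logistic models (SAP 3.4.3.3).

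**4. Planned checks.** The three numbered sensitivity analyses in SAP 3.4.3.1 vary the stratification factors and the handling of intercurrent events. None varies the baseline, and no count of post-dose baselines is planned.

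**5. Size, for illustration.** Let
- f = share of patients whose baseline entry is post-dose (assumed 5% to 30%);
- d = epetraborole-minus-placebo shift in those entries (assumed 1 to 5 points);
- b = slope of Month 6 score on baseline (assumed 0.5 to 0.7).

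Late entries move the between-arm difference in mean baseline by f × d. The change score loses f × d, and covariate adjustment gives back (1 − b) × f × d. The net shift in the treatment difference is −b × f × d.

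- Smallest: −0.5 × 0.05 × 1 = −0.025 points.
- Middle: −0.7 × 0.10 × 2 = −0.14 points.
- Largest: −0.7 × 0.30 × 5 = −1.05 points.

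A simulation of 2,000 trials (124 versus 62 patients, assumed SD 18, b = 0.6, f = 30%, d = 3, true effect 5) gave a mean estimate of 5.11 with pre-dose baselines and 4.58 with the SAP rule. The difference is −0.54, matching −0.6 × 0.30 × 3 = −0.54.

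The sign depends on d. Early benefit on drug (d > 0) shrinks the estimated effect; early worsening (d < 0) inflates it.

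**6. Plausibility of the upper end.** QOL-B recall is one week (Protocol 7.5.2 is silent on this; see 7.5.5.2), so roughly 1 of 7 recalled days is post-dose in a Day 2 entry. If patients weighted the days evenly, d = 5 would need a between-arm difference of about 5 × 7 = 35 points on that one day. Patients may weight the latest day more heavily, but the upper end still looks remote.

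**The case against.** The strongest reply is that the window is administrative. Between screening and Day 2 only two QOL-B forms are scheduled, so taking the last entry mainly selects the Day 1 form over the screening form. The SAP revision history for version 2.0 describes the change as a clarification of entries belonging to the Day 1 visit. Late forms should be few, recall is one week, the trial is double-blind, and the rule is the same in both arms. All of that stands, and it is why the effect is probably small. It does not answer the drafting point: as written, a later edit outranks a valid pre-dose score, and the protocol says otherwise.

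A reader might also infer more than the documents support:

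- **That patients could be analysed on a US primary baseline that fails the entry criterion.** Inclusion criterion 3.b rests on MACrO₂ symptoms. QOL-B is not an eligibility measure. The mismatch could arise only in MACrO₂ item severities, where the protocol says the "symptom identified on Day 1, will be defined as the baseline assessment for determination of clinical response in postbaseline visits"; key-symptom response is no longer the US primary.
- **That early gastrointestinal events would distort the primary.** A respiratory domain does not measure them; digestive symptoms are a separate NTM Module domain.
- **That the six-day CGIS window touches the primary.** It affects only secondary CGIS and CGIC analyses, outside multiplicity control.
- **That the SAP's internal conflict invalidates the Phase 3 rule.** The Phase 2 definition concerns another instrument and phase. It shows inconsistency, not error in the QOL-B analysis.

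**Conclusion.** The point stands as a departure from the protocol that the SAP does not declare. The baseline of the US primary endpoint and of the MACrO₂ total scaled score is not guaranteed to precede treatment, and a valid pre-dose score can be displaced. No material bias is shown. The illustrated shift of about 0.03 to 1.05 points rests wholly on assumed f, d and b, and the upper end combines 30% post-dose baselines with a 5-point differential within a day of dosing, neither of which is documented. For scale only, the SAP's within-patient response thresholds for this score are 8 and 11.1 points. The case for acting is that the baseline of a confirmatory change score should be secured by rule, and this is easily done.

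**What to change.** **SAP 3.1.2 and 3.4.3.1.**
1. Use the Day 1 entry completed before first dose whenever one exists; a later edit does not replace it.
2. Only if there is none, use the Day 1 form entered up to first dose + 1 day (for CGIS, up to + 6 days), and flag it.
3. Report the number of flagged baselines by arm and instrument.
4. Correct the CGIS sentence, which describes a site-entered scale as the "last entry recorded by the patient on or prior to the first dose of study drug + 6 days".

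**Sensitivity analysis.** Repeat the US primary with flagged QOL-B baselines replaced by the Day -14 to -7 score. This should stay a sensitivity analysis: patients whose background regimen had stopped restart it at Screening, so that score may precede a settled regimen. CGIS is not among the instruments that Protocol 7.5.5 schedules twice before dosing, so no such substitute exists for it.

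**SAP Section 5.** List the remaining departure from Protocol 7.5.5. The Phase 2 wording in 3.4.1.1 need only be noted, since SAP Section 1 limits later changes to Phase 3.

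**Cost.** A few sentences, a modest re-derivation from ePRO entry times, and one extra run. This assumes the ePRO system stores entry times and values before any edit; neither document says so. The change is cleanest before Phase 3 unblinding; after that, SAP Section 1 would put it in a post hoc addendum or the CSR.

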5.8.3. Prohibited Prior and Concomitant Therapy

The following medications and treatments are prohibited:

- Any anticipated or planned lung surgery for MAC lung disease
- Immunosuppressive therapy use at Screening and throughout the Treatment Period that in the opinion of the Investigator may place the patient at risk for an opportunistic pulmonary infection, including transplant rejection medication and chronic systemic corticosteroids defined as ≥ 20 mg/day of prednisone or systemic equivalent for >4 weeks. Short-term use of corticosteroids (eg, glucocorticoid taper for treatment of COPD exacerbation) is allowed.
- Chemotherapy or radiation therapy within 1 year prior to randomization through the LFU Visit

- The addition of a new non-study-specific, antimycobacterial therapy (eg, macrolides, rifamycins, ethambutol, aminoglycosides, fluoroquinolones, oxazolidinones, trimethoprim-sulfamethoxazole, clofazimine, isoniazid) to treat the index MAC infection is not allowed for reasons other than microbiological failure.

If the Investigator believes that a potentially MAC-active agent is required to treat a non-MAC infection, the case should be discussed with the Medical Monitor prior to administration. Premature discontinuation of study drug or withdrawal from study should be avoided in these cases. See [Section 5.7](#) for OBR details.

- Participation in a clinical trial of an investigational agent within 30 days (or 5 half-lives, whichever is longer) prior to Screening and throughout the Treatment Period

The use of concomitant drugs with the potential to cause anemia should be avoided when feasible. Any questions regarding the use of concomitant non-study-specific therapy should be directed to the Medical Monitor prior to administration.

Any patient who receives prohibited therapy will be excluded from the Per-Protocol Population; see the SAP(s) for more details.

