Phase 3: No data are available on symptom-based clinical response or minimal clinically important differences (MCIDs) using available PROs in patients with treatment-refractory MAC lung disease; therefore, previously published Month 6 sputum culture conversion rates in treatment-refractory MAC lung disease were used to initially estimate the number of patients expected to have an MCID improvement in PRO score, assuming a correlation between microbiological response and clinical symptom improvement. A Phase 3 study comparing ALIS + OBR versus OBR alone in patients with treatment-refractory MAC lung disease reported Month 6 sputum culture conversion rates of 29.0% compared with 8.9%, respectively, in the ITT population. Therefore, the initial sample size estimate for the Phase 3 part of the study assumes that the true number of patients experiencing an MCID improvement in PRO score is 30% for the epetraborole + OBR arm and 10% for the placebo + OBR arm. Assuming a 2:1 randomization and a 2-sided alpha of 0.05, a Phase 3 study of 186 patients with proven MAC lung disease (ie, in the Micro-ITT population) in the primary analysis (124 patients in the epetraborole + OBR arm and 62 patients in the placebo + OBR arm) would provide approximately 90% power, while also assuming when performing an analysis of proportions using the method of Miettinen and Nurminen. The total sample size for the Phase 3 part of the study is estimated to be 234 patients (156 patients in the epetraborole + OBR arm and 78 patients in the placebo + OBR arm) rather than 186 patients, to allow for approximately 20% of randomized patients to be excluded from the Micro-ITT Population due to lack of a study qualifying baseline culture (see Inclusion Criterion 3.a in Protocol Section 4.1); therefore, 186 patients are expected to be included in the Micro-ITT Population for the primary efficacy analysis. The sample size for Phase 3 will be reassessed after Phase 2 analyses, which will be based on data for all patients in Phase 2 through Month 6. Any needed sample size adjustment for Phase 3 will be determined by the Sponsor as part of the review of unblinded results from the fully independent Phase 2 data.

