2. Treatment: Epetraborole oral tablets 500 mg (two 250 mg oral tablets) QD + OBR or placebo oral tablets QD matched to epetraborole dosage + OBR
3. Variable: Sputum conversion rate is defined as proportion of patients having culture conversion based on 3 consecutive monthly negative sputum cultures for MAC by Month 6
4. Intercurrent events:
 - a. New, additional non-study-specific, antimycobacterial therapy that is potentially effective against MAC for reasons other than clinical failure of study drug: data collected after such therapy will not be used and patients will be classified as a failure for microbiological response (composite strategy)
 - b. Surgery for MAC lung disease for reasons other than clinical failure of study drug: data collected after such surgery will not be used and patients will be classified as a failure for microbiological response (composite strategy)
 - c. Permitted medications/interventions and or prohibited medications/interventions other than those described in bullets a and b: microbiological response data collected after permitted or other prohibited medications/interventions administration will be used as recorded (treatment policy strategy)
 - d. Inadequate compliance: patient data will be used as recorded (treatment policy strategy)

5. Population-level summary: Difference between epetraborole + OBR and placebo + OBR in sputum conversion rate by Month 6.

“Microbiological response” is defined as sputum culture conversion based on 3 consecutive monthly negative sputum cultures for MAC by Month 6. By-patient microbiological response will be presented for the Micro-ITT Population by Month 6. Descriptive statistics (n, %) will be presented by treatment group, along with the treatment difference (i.e. epetraborole + OBR response percentage minus placebo + OBR response percentage), associated 95% confidence interval and p-value, calculated using the method of Miettinen and Nurminen, both including (primary analysis) and excluding (sensitivity analysis) stratification by baseline ALIS use and the presence or absence of any fibrocavitary disease.

3.4.3.3 *Secondary Efficacy Endpoints*

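### Both Phase 3 estimands override data after incidental MAC-active therapy, yet by default use data as they stand after therapy or surgery given for clinical failure, a term the SAP does not define

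*SAP*

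**What the plan says.** SAP 3.4.3.1 (QOL-B respiratory domain, primary in the US) and 3.4.3.2 (culture conversion, primary elsewhere) list the same intercurrent events.

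- Event (a) is "New, additional non-study-specific, antimycobacterial therapy that is potentially effective against MAC for reasons other than clinical failure of study drug". Event (b) is MAC lung surgery with the same limit on reason. For conversion, both make the patient a failure. For QOL-B, both replace later data with the last score before the event. Both treatments are labelled composite.
- Event (c) takes every other permitted or prohibited medication or intervention. For QOL-B, "QOL-B respiratory domain data collected after permitted or other prohibited medications/interventions administration will be used as recorded"; for conversion, "microbiological response data collected after permitted or other prohibited medications/interventions administration will be used as recorded".

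SAP 3.4.3.3 applies the QOL-B rules to the MACrO₂ total scaled score, so all three hierarchically tested endpoints (SAP 3.4) are involved.

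Protocol 5.8.3 uses a different term: adding a new antimycobacterial for the index infection "is not allowed for reasons other than microbiological failure". Under Protocol 5.7.2, a patient needing such rescue stops study drug and stays in the study for the End of Therapy (EOT) and Late Follow-up (LFU) assessments.

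**The concern.** Starting new MAC treatment because the assigned regimen has failed is strong evidence of an unfavourable outcome. An antibiotic given for an unrelated infection says little about study drug. As written, the second is overridden and the first is not. An undefined label, clinical failure, decides which rule a patient meets. At stake is whether each regional primary estimand describes the effect of epetraborole + OBR, and whether the choice is made before or after Phase 3 is unblinded.

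**Working it through.** **1. Where each case lands, reading the bullets literally**

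| Case | Culture conversion | QOL-B respiratory domain, MACrO₂ total scaled score |
|---|---|---|
| New MAC-active drug or MAC surgery, not for clinical failure | (a)/(b): failure | (a)/(b): last prior score carried forward |
| The same, for clinical failure | (c): unchanged | (c): unchanged; if Month 6 is missing, dropped under MAR |
| New drug for microbiological failure | (a), as a reason other than clinical failure | (a) |

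**2. Two patients, both culture-negative at Months 1, 2 and 3.** At Month 5, A receives a MAC-active antibiotic for a non-MAC infection: event (a), failure. B starts new MAC therapy for clinical failure: event (c), so the three negatives stand and B is a success. No post-rescue data are needed for this result.

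**3. The composite label.** Carrying the last score forward keeps any gain already made. For the continuous scores, (a) and (b) are last observation carried forward, with no unfavourable value assigned.

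**4. Sensitivity analyses.** Analysis 1 only drops the stratification factors. Analyses 2 and 3 extend unchanged use to the (a) and (b) patients. None treats therapy for failure as unfavourable.

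**5. What can be credited after rescue.** EOT falls within 7 days of the last dose and LFU 84 ± 14 days after it (Protocol 3.1). These two scheduled cultures cannot supply three consecutive monthly negatives. Missing cultures that prevent assessment count as non-response (SAP 3.1.4), apart from patients who were previously negative and cannot produce sputum. New conversions after rescue will seldom be credited.

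**6. The plan's power, as a base for illustration.** Inputs from SAP 2.2.7: "Assuming a 2:1 randomization and a 2-sided alpha of 0.05"; the true response "is 30% for the epetraborole + OBR arm and 10% for the placebo + OBR arm"; "124 patients in the epetraborole + OBR arm and 62 patients in the placebo + OBR arm) would provide approximately 90% power". With pooled p̄ = (62×0.10 + 124×0.30)/186 = 0.2333:

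- SE under no difference = √[0.2333×0.7667×(1/62 + 1/124)] = 0.0658
- SE under the alternative = √[0.10×0.90/62 + 0.30×0.70/124] = 0.0561
- Power = Φ[(0.20 − 1.96×0.0658)/0.0561] = Φ(1.27) = 89.7%

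Exact enumeration of the unstratified Miettinen-Nurminen test gives 90.7%. The stated figure reproduces.

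**7. Hypothetical dilution of conversion.** Assume, against step 5, that post-rescue monthly cultures exist. Let f be the share of placebo non-converters rescued, f/2 the share on epetraborole, and c the conversion rate after rescue. Then placebo = 0.10 + 0.90·f·c and epetraborole = 0.30 + 0.70·(f/2)·c. With c = 29% (the rate SAP 2.2.7 cites for ALIS + OBR) and the approximation in step 6:

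| f | Placebo | Epetraborole | Power |
|---|---|---|---|
| 5% | 11.3% | 30.5% | 85.7% |
| 10% | 12.6% | 31.0% | 81.1% |
| 20% | 15.2% | 32.0% | 70.7% |

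Equal shares in both arms give 87.3%, 84.9% and 79.7%. Keeping f/2 on epetraborole and varying c from 10% to 50%, power runs from 88.4% (f = 5%, c = 10%) to 54.3% (f = 20%, c = 50%).

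**8. Hypothetical dilution of QOL-B.** Shift = gain × (placebo share − epetraborole share), assuming a Month 6 score is recorded after rescue. Gains of 8 to 11.1 points (the SAP's two response thresholds), with 5% to 20% of placebo patients rescued and half that share on epetraborole, give 8×0.025 = 0.2 to 11.1×0.10 = 1.1 points. If only placebo patients are rescued, the range is 0.4 to 2.2 points.

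**The case against.** The tempting stronger reading is that the rule is inverted throughout: rescue benefit is systematically credited to the randomised arm on both primaries, with a material loss of power. The documents do not support it.

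- The only rescue that Protocol 5.8.3 allows is for microbiological failure. Read literally, this falls under (a), so the gap is certain only for therapy or surgery labelled clinical failure.
- Scheduled data after rescue seldom permit a new conversion. A QOL-B credit needs a recorded Month 6 score, and the SAP has no rule mapping EOT or LFU to Month 6.
- Both primaries are read by Month 6, cultures can take up to 8 weeks to report (Protocol 3.1.1), and anticipated new antimycobacterial therapy is an exclusion criterion. Nothing supports a 10% to 20% rescue rate in that window.
- The trial was terminated, so 124 and 62 are planning numbers. Phase 2 conversion was not superior (SAP 1), so more rescue on placebo is an assumption.
- Therapy prohibited by Protocol 5.8.3 removes a patient from the Per-Protocol population, which is a stated QOL-B sensitivity analysis.
- Treatment policy is a legitimate strategy. SAP 3.3.6 uses the same phrase about reasons when describing antibiotics for non-MAC infections, which suggests that the authors had confounding antibiotics in mind.

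These points limit the size and rule out the stronger reading. They leave the gap in place. Per-Protocol exclusion does not count failure as failure. Treatment policy reaches these patients through residual wording, not a declared choice. Patient B remains a success without any post-rescue culture. The two unreconciled terms make the classification less certain.

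**Conclusion.** The rule is wrong as written, within limits. On conversion, therapy or surgery for clinical failure is scored more leniently than an incidental MAC-active antibiotic. On QOL-B and the MACrO₂ total scaled score, such a patient is either analysed unchanged or, without a Month 6 value, dropped as missing at random although the reason is informative. Neither route is unfavourable.

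The likely effect is some dilution of the treatment difference rather than a false claim of benefit. That direction assumes that failure is at least as common on placebo. The size cannot be derived: the documents give no rescue rate, no conversion rate after rescue, and no SD or effect size for QOL-B. The figures in steps 7 and 8 show sensitivity to assumed values. They do not estimate what will happen in this trial, and for conversion they presuppose cultures that the schedule does not name.

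**What to change.** Before Phase 3 unblinding:

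1. In SAP 3.4.3.2 and for all responder endpoints, extend (a) and (b) to new MAC-active therapy or surgery for the index MAC infection because of clinical or microbiological failure. Count these cases as failure and exclude them expressly from (c).
2. Define clinical failure of study drug for the analysis, and reconcile it with microbiological failure in Protocol 5.8.3, so that classification does not rest on an undefined label.
3. For QOL-B and the MACrO₂ total scaled score, bring these cases under an explicit rule and correct the composite label on (a) and (b). Add a sensitivity analysis that assigns a no-benefit value, for example the worse of the baseline and last pre-event scores. That value is one defensible choice among several, so it belongs in a sensitivity analysis. Sensitivity analyses 2 and 3 can stay.

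The cost is some SAP wording and a little more programming, with no new data. The downside is that a few patients move to failure or no change.
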